11.2. Reporting to the Institutional Review Board (IRB)

Investigative sites within DF/HCC and DF/PCC will report SAEs directly to the DFCI Office for Human Research Studies (OHRS) per the DFCI IRB reporting policy.

Other investigative sites will report SAEs to their respective IRB according to the local IRB's policies and procedures in reporting adverse events. A copy of the submitted institutional SAE form should be forwarded to the Overall PI within the timeframes detailed in the table below.

Attribution	DF/HCC Reportable AEs				
	Gr. 2 & 3 AE Expected	Gr. 2 & 3 AE Unexpected	Gr. 4 AE Expected	Gr. 4 AE Unexpected	Gr. 5 AE Expected or Unexpected
Unrelated Unlikely	Not required	Not required	5 calendar days [#]	5 calendar days	24 hours*
Possible Probable Definite	Not required	5 calendar days	5 calendar days [#]	5 calendar days	24 hours*
# If listed in protocol as expected and not requiring expedited reporting, event does not need to be reported.					

* For participants enrolled and actively participating in the study **or** for AEs occurring within 30 days of the last intervention, the AE should be reported within 24 business hours of learning of the event.

The Overall PI will submit SAE reports from outside institutions to the DFCI OHRS according to DFCI IRB policies and procedures in reporting adverse events.

11.3. Reporting to Hospital Risk Management

Participating investigators will report to their local Risk Management office any subject safety reports or sentinel events that require reporting according to institutional policy.

11.4. Reporting SAEs to EISAI

All SAEs, as defined in Section 11.1.2, will be reported to EISAI on a Medwatch 3500A form within one business day of the event. The reports will be sent to EISAI at the number listed below:

EISAI safety [contact]) Email: [contact]

External participating sites will send Medwatch 3500A reports directly to EISAI, and a copy will be sent to the DFCI project manager: [contact]

DF/HCC sites will send the Medwatch 3500A reports directly to EISAI and file a copy in the study regulatory documents.

11.5. Monitoring of Adverse Events and Period of Observation

All adverse events, both serious and non-serious, and deaths that are encountered from initiation of study intervention, throughout the study, and within 30 days of the last study intervention should be followed to their resolution, or until the participating investigator assesses them as stable, or the participating investigator determines the event to be irreversible, or the participant is lost to follow-up. The presence and resolution of AEs and SAEs (with dates) should be documented on the appropriate case report form and recorded in the participant's medical record to facilitate source data verification.

For some SAEs, the investigator or designee may follow-up by telephone, fax, and/or monitoring visit to obtain additional case details deemed necessary to appropriately evaluate the SAE report (e.g., hospital discharge summary, consultant report, or autopsy report).

Participants should be instructed to report any serious post-study event(s) that might reasonably be related to participation in this study. Participating investigators should notify the DF/HCC Overall Principal Investigator and their respective IRB of any unanticipated death or adverse

event occurring after a participant has discontinued or terminated study participation that may reasonably be related to the study.

12. DATA AND SAFETY MONITORING

This study will be organized, performed, and reported in compliance with the protocol, standard operating practices, working practice documents, and applicable regulations and guidelines. Site visit audits may be made periodically by a qualified compliance auditing team, which is an independent function from the study conduct team.

12.1. Data Reporting

Method

The QACT will collect, manage, and monitor data for this study.

Data Submission

The schedule for completion and submission of case report forms (paper or electronic) to the QACT is as follows:

Form	Submission Timeline
Eligibility Checklist	Complete prior to registration with QACT
On Study Form	Within approximately 14 days of registration
Baseline Assessment Form	Within approximately 14 days of registration
Treatment Form	Within approximately 10 days of the last day of the cycle
Adverse Event Report Form	Within approximately 10 days of the last day of the cycle
Response Assessment Form	Within approximately 10 days of the completion of the cycle required for response evaluation
Off Treatment/Off Study Form	Within approximately 14 days of completing treatment or being taken off study for any reason
Follow up/Survival Form	Within approximately 14 days of the protocol defined follow up visit date or call

12.2. Safety Meetings

The DF/HCC Data and Safety Monitoring Committee (DSMC) will review and monitor toxicity and accrual data from this trial. The committee is composed of clinical specialists with experience in oncology and who have no direct relationship with the study. Information that raises any questions about participant safety will be addressed with the Principal Investigator and study team.

The DSMC will meet quarterly and/or more often if required to review toxicity and accrual data. Information to be provided to the committee may include: up-to-date participant accrual; current dose level information; DLT information; all grade 2 or higher unexpected adverse events that have been reported; summary of all deaths occurring within 30 days for Phase I or II protocols; for gene transfer protocols, summary of all deaths while being treated and during active follow-up; any response information; audit results, and a summary provided by the study team. Other information (e.g. scans, laboratory values) will be provided upon request.

12.3. Monitoring

Involvement in this study as a participating investigator implies acceptance of potential audits or inspections, including source data verification, by representatives designated by the DF/HCC Overall Principal Investigator or DF/HCC. The purpose of these audits or inspections is to examine study-related activities and documents to determine whether these activities were conducted and data were recorded, analyzed, and accurately reported in accordance with the protocol, institutional policy, and any applicable regulatory requirements. Please refer to Appendix 9: Section 5.0 for additional information.

All data will be monitored for timeliness of submission, completeness, and adherence to protocol requirements. Monitoring will begin at the time of participant registration and will continue during protocol performance and completion.

12.4. Multicenter Guidelines

This protocol will adhere to the policies and requirements of the DF/HCC Multi-Center Data and Safety Monitoring Plan. The specific responsibilities of the Overall PI, Coordinating Center, and Participating Institutions and the procedures for auditing are presented in Appendix F.

The Overall PI/Coordinating Center is responsible for distributing all IND Action Letters or Safety Reports to all participating institutions for submission to their individual IRBs for action as required.

Mechanisms will be in place to ensure quality assurance, protocol compliance, and adverse event reporting at each site.

Except in very unusual circumstances, each participating institution will order the study agent(s) directly from supplier. A participating site may order the agent(s) only after the initial IRB approval for the site has been forwarded to the Coordinating Center.

13. REGULATORY CONSIDERATIONS

13.1. Protocol Review and Amendments

This protocol, the proposed informed consent and all forms of participant information related to the study (e.g., advertisements used to recruit participants) and any other necessary documents must be submitted, reviewed and approved by a properly constituted IRB governing each study location.

Any changes made to the protocol must be submitted as amendments and must be approved by the IRB prior to implementation. Any changes in study conduct must be reported to the IRB. The DF/HCC Overall Principal Investigator (or Protocol Chair) will disseminate protocol amendment information to all participating investigators.

All decisions of the IRB concerning the conduct of the study must be made in writing.

13.2. Informed Consent

All participants must be provided a consent form describing this study and providing sufficient information for participants to make an informed decision about their participation in this study. The formal consent of a participant, using the IRB approved consent form, must be obtained before the participant is involved in any study-related procedure. The consent form must be signed and dated by the participant or the participant's legally authorized representative, and by the person obtaining the consent. The participant must be given a copy of the signed and dated consent document. The original signed copy of the consent document must be retained in the medical record or research file.

13.3. Ethics

This study is to be conducted according to the following considerations, which represent good and sound research practice:

- US Code of Federal Regulations (CFR) governing clinical study conduct and ethical principles that have their origin in the Declaration of Helsinki
 - Title 21 Part 50 – Protection of Human Subjects
www.access.gpo.gov/nara/cfr/waisidx_02/21cfr50_02.html

- Title 21 Part 54 – Financial Disclosure by Clinical Investigators
www.access.gpo.gov/nara/cfr/waisidx_02/21cfr54_02.html
- Title 21 Part 56 – Institutional Review Boards
www.access.gpo.gov/nara/cfr/waisidx_02/21cfr56_02.html
- State laws
- DF/HCC research policies and procedures
<http://www.dfhcc.harvard.edu/clinical-research-support/clinical-research-unit-cru/policies-and-procedures/>

It is understood that deviations from the protocol should be avoided, except when necessary to eliminate an immediate hazard to a research participant. In such case, the deviation must be reported to the IRB according to the local reporting policy.

13.4. Study Documentation

The investigator must prepare and maintain adequate and accurate case histories designed to record all observations and other data pertinent to the study for each research participant. This information enables the study to be fully documented and the study data to be subsequently verified.

Original source documents supporting entries in the case report forms include but are not limited to hospital records, clinical charts, laboratory and pharmacy records, recorded data from automated instruments, microfiches, photographic negatives, microfilm or magnetic media, and/or x-rays.

13.5. Records Retention

All study-related documents must be retained for the maximum period required by applicable federal regulations and guidelines or institutional policies.

14. STATISTICAL METHODS

14.1. Statistical and Analytical Plans

Statistical programming and analyses will be performed using SAS and other validated statistical software as required.

The primary analyses of efficacy endpoints that are related to tumor assessment will be performed using investigator-assessed data.

The full analysis dataset will include all subjects who receive at least one dose of study treatment. Objective response will be assessed according to RECIST 1.1. All patients who receive at least one dose of therapy will be included in the calculation of objective response rate. Patients who, in retrospect, do not have measurable disease, and patients with no follow up evaluation of response, will be considered non-responders for the purpose of analysis of the primary endpoint. Confirmation of response is required to assign a status of best overall response of CR or PR.

Patients who have developed metastatic disease within 12 months of last dose of (neo) adjuvant chemotherapy who enroll on protocol will be considered in the analysis as a second-line patient, even if no prior chemotherapy was received in the metastatic setting.

Demographic and Other Baseline Characteristics

Demographic and other baseline characteristics will be listed, and summarized for the full analysis dataset. For continuous demographic/baseline variables such as age, weight, and vital signs, results will be summarized and presented as number (N), mean, median, and range. For categorical variables such as race/ethnicity, the number and percentage of subjects will be used.

Subject Disposition

The number and percentage of subjects, who complete or prematurely withdraw from the study, as well as the reason for discontinuation, will be summarized.

14.2. Determination of sample size

The historical ORR data for chemotherapy in the first-line metastatic setting indicated a 33% ORR for anthracycline and 38% ORR for taxanes. For patients treated beyond first-line, the historical data indicate an approximate 20% ORR. This trial will be open for treatment in either the first- or second-line setting. The study primary endpoint is the ORR of eribulin given as monotherapy. ORR defined as the proportion of subjects who achieve a confirmed CR or PR (RECIST 1.1), will be evaluated for each cohort separately using investigator-assessed data (Appendix 1).

Statistical considerations for eribulin monotherapy cohorts (cohort 1 and 2)

ORR will be estimated separately for the HR+/HER2- and the TNBC monotherapy cohorts. For the TNBC cohort, it is assumed there will be a 50-50 allocation between first- and second-line patients. For the HR-positive cohort, it is assumed there will be a 40-60 allocation between first- and second-line patients. The primary objective is to estimate the response rate (by RECIST 1.1) to eribulin.

From the meta-analysis of O’Shaughnessy *et al*, the ORR in TNBC in the first-line setting was approximately 23%, and was 18% in the second-line setting based on the results of the TNBC subgroup of patients in the RIBBON-2 trial. With a 50-50 allocation between first- and second-line patients, we would assume a response rate of approximately 21-22% in the cohort of TNBC. For patients with HR-positive disease, the estimated ORR from RIBBON-2 was 29.6% in the second-line setting and has been reported to be between 33-38% for first-line therapy. We assume a 40-60 allocation between first- and second-line patients in the HR-positive cohort, and conservatively estimate a response rate of 30% in this protocol.

Our response rate assumptions for this protocol are 22% in the TNBC cohort and 30% in HR-positive cohort. Because eribulin has already demonstrated activity, including an overall survival advantage in the refractory setting, this study will utilize a single-stage design. The sample sizes of each cohort were based on the lower bounds of the 90% exact confidence intervals (CI) around possible observed response rates, as shown in the Table 5.

Table 5: Eribulin Sample Size Table

*Confidence intervals estimated using exact binomial methods.

Sample Size (per cohort)	Number responses	Observed response rate	Lower end 90% CI*	Upper end 90% CI*	Width 90% CI
45	9	.200	.109	.323	.215
	11	.244	.144	.372	.228
	13	.289	.180	.420	.239
	14	.311	.199	.443	.244
	15	.333	.218	.466	.248
	16	.356	.237	.489	.252
	17	.378	.257	.511	.254
	18	.400	.277	.534	.257
	19	.422	.297	.555	.258
	20	.444	.317	.578	.261
	21	.467	.338	.599	.261

For TNBC (orange) cohort, if 16 or more women of 45 have a response, then the lower bound of the 90% exact confidence interval of the observed response rate exceeds 22%.

For ER+ (yellow) cohort, if 20 or more women of 45 have a response, the lower bound of the 90% exact confidence interval of the observed response rate exceeds 30%, which is the historical response rate of the combined 1st and 2nd line groups.

In the TNBC cohort, there will be 90% power to detect a 22% percent improvement in response (22% vs. 44%) assuming an equal allocation of first- and second-line patients. In the HR-positive cohort, there will be 90% power to detect a 23 percent improvement in response (30% vs. 53%) assuming first- and second-line patients are allocated approximately 40-60. Both calculations assume a two-sided, 0.1 type-1 error and an exact binomial test.

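### Section 14.2 calls 30% the combined historical response rate for the HR-positive cohort, but its own inputs blend to 31.0–33.0%

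*Combined protocol and SAP*

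**What the plan says.** All of this is in section 14.2 (Determination of sample size).

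**HR-positive.** The inputs are given in one sentence: "the estimated ORR from RIBBON-2 was 29.6% in the second-line setting and has been reported to be between 33-38% for first-line therapy". The first-line range matches the general rates that open the section: "The historical ORR data for chemotherapy in the first-line metastatic setting indicated a 33% ORR for anthracycline and 38% ORR for taxanes". The benchmark follows: "We assume a 40-60 allocation between first- and second-line patients in the HR-positive cohort, and conservatively estimate a response rate of 30% in this protocol". After Table 5, the text says that with 20 or more responders of 45 the lower 90% exact limit "exceeds 30%, which is the historical response rate of the combined 1st and 2nd line groups". The power statement then takes 30% as the null against 53%, with 90% power, a two-sided 0.1 type-1 error, an exact binomial test and an approximate 40-60 allocation.

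**TNBC.** The first-line rate is given as about 23%, and the rate "was 18% in the second-line setting based on the results of the TNBC subgroup of patients in the RIBBON-2 trial". At a 50-50 allocation the section concludes: "we would assume a response rate of approximately 21-22% in the cohort of TNBC". It carries 22% forward, with 16/45 as the reference count and 22% vs. 44% in the power statement. The opening paragraph also has a general later-line figure: "For patients treated beyond first-line, the historical data indicate an approximate 20% ORR".

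The section states that the primary objective is to estimate the response rate.

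**The concern.** Each cohort is a single arm, so the historical rate is the only comparator. The sentence after Table 5 is a factual label: it says 30% is what history shows for the combined lines. If the plan's own inputs give a higher figure, a result of 20/45 could be described as exceeding the combined historical rate when its lower limit does not.

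The direction also matters. A low figure is cautious when it projects how many patients will respond. The same low figure used as a null is easier to exceed, so there it is lenient.

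**Working it through.** **1. The plan's own figures reproduce.** For x responders of 45, the exact (Clopper-Pearson) 90% lower limit is the 5th percentile of a Beta(x, 46 − x) distribution.

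- HR-positive: 19/45 gives 29.7% and 20/45 gives 31.7%, so 20 is the smallest count above 30%. P(X ≥ 20 | 30%) = 2.8%; P(X ≥ 20 | 53%) = 90.3%.
- TNBC: 15/45 gives 21.8% and 16/45 gives 23.7%, so 16 is the smallest count above 22%. P(X ≥ 16 | 22%) = 2.6%; P(X ≥ 16 | 44%) = 90.3%.

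Counts and power are therefore right for the benchmarks as entered. The question is where the benchmarks come from.

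**2. HR-positive blend.** Blend = 0.4 × first-line + 0.6 × second-line.

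- First-line 33%: 0.4 × 33 + 0.6 × 29.6 = 13.2 + 17.76 = 30.96%.
- First-line 38%: 0.4 × 38 + 0.6 × 29.6 = 15.2 + 17.76 = 32.96%.

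**3. What 30% would need.**

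- At 40-60, the first-line rate would have to be (30 − 17.76) / 0.4 = 30.6%, below the cited range.
- At the cited rates, the first-line share would have to be (30 − 29.6) / (33 − 29.6) = 11.8%, or (30 − 29.6) / (38 − 29.6) = 4.8%. That is about 5 or 2 of 45 patients. The planned share is 0.4 × 45 = 18, so an approximate allocation does not explain the gap.

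**4. Effect on the reference count.** The 20/45 lower limit (31.73%) equals the blend when first-line = (31.73 − 17.76) / 0.4 = 34.9%.

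| First-line rate | Blend | P(X ≥ 20) at the blend | Smallest count whose lower limit exceeds the blend | Upper tail for that count |
|---|---|---|---|---|
| 33% | 30.96% | 3.9% | 20 | 3.9% |
| 35.5% (midpoint) | 31.96% | 5.4% | 21 | 2.8% |
| 38% | 32.96% | 7.2% | 21 | 3.9% |

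The nominal upper tail is 5%, half of the two-sided 0.1. The lower limit for 21/45 is 33.8%.

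**5. Power.** This depends on what is held fixed, and the plan does not say.

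- Improvement held at 23 points: 31.0% vs. 54.0% with 20/45 gives 92%; 33.0% vs. 56.0% with 21/45 gives 92%. Across the whole 33–38% range it is 89–94%.
- Alternative held at 53%: 20/45 gives 90% and 21/45 gives 84%.

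**6. TNBC.** 0.5 × 23 + 0.5 × 18 = 20.5%. The smallest count whose lower limit exceeds 20.5% is 15/45 (upper tail 3.1%); keeping 16/45 gives 1.4%. With the general 20% later-line rate in place of 18%, the blend is 0.5 × 23 + 0.5 × 20 = 21.5%, again with 15/45 (upper tail 4.5%).

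**The case against.** **The plan openly calls 30% a conservative estimate.** Where 30% is introduced, it is offered as an estimate and not as a weighted mean, and rounding an expected rate down is ordinary practice. That is fair for that sentence. It does not cover the sentence after Table 5, which drops the qualifier, calls 30% historical and reads the lower limit against it.

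**The inputs are rough.** The first-line range repeats general anthracycline and taxane figures. Section 2.2 gives wider ranges still: 30–60% first-line and 20–30% after progression. A first-line rate of 30% would give 0.4 × 30 + 17.76 = 29.8%. The general 20% later-line rate would give 0.4 × 33 + 0.6 × 20 = 25.2% up to 0.4 × 38 + 0.6 × 20 = 27.2%, and against those 30% is strict. What stands is that the 31–33% blend is no more precise than its inputs. It does not rescue the label, because 14.2 names 29.6% and 33–38% for this cohort and none of the other figures.

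**The aim is estimation.** The text around Table 5 justifies a sample size, and no decision is tied to a count. This stands in full and limits the weight of the point.

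**TNBC.** The first-line input is only approximate, and 20.5% can be rounded to 21%, the low end of the stated range. Rounding does not reach 22%.

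**Conclusion.** The HR-positive label is contradicted by the section's own numbers: every first-line rate in the cited range blends to more than 30%, and the benchmark is 1.0 to 3.0 points low. The reference count of 20/45 still clears the blend in the lower part of the range and falls one responder short above about 34.9%. This is minor. It rests on the cited rates, the 40-60 allocation and exact binomial methods with n = 45.

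A reader might infer more, and the documents do not support it:

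- *That the trial has a faulty success rule with inflated error.* No go/no-go rule is attached to the counts. The 5.4% and 7.2% tails describe how 20/45 reads against a blend of 32.0% or 33.0%; they are not the error rate of a planned decision.
- *That 20/45 never exceeds the combined historical rate.* At a first-line rate of 33% it does.
- *That the cohort is undersized or its estimate affected.* The sample size, the observed rate and its interval do not depend on the benchmark. Power drops to 84% only if the count moves to 21 and the alternative stays at 53%.
- *That the TNBC benchmark invites the same overclaim.* It is 1.5 points above the blend of its cited inputs, so it is stricter and no overclaim follows. The plan itself states 21–22% there; 20.5% is what its cited rates give.

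**What to change.** In section 14.2 only, show the weighted calculation for each cohort.

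**HR-positive, one of two:**

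- Keep 30% and 20/45, but describe 30% as a chosen reference value, give the reason for it, and note that it lies below the 31–33% blend of the stated inputs. Drop the word conservatively, and do not describe 20/45 as exceeding the combined historical rate. This changes wording only.
- Name one first-line rate and carry it through: 33% gives 31.0% and 20/45; 38% gives 33.0% and 21/45. State what is held fixed for power: about 92% if the 23-point improvement is kept, or 84% for 21/45 if the alternative stays at 53%. The reference count rises by one responder if the named rate is above about 34.9%.

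**TNBC, as a note:** correct the blend to 20.5% and label 22% (16/45) as a deliberately stricter reference. If the 20% later-line rate was intended, cite it in place of 18% and state 21.5%.

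Neither change adds patients or procedures or alters the sample size.
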